11. ADVERSE EVENT REPORTING

Timely, accurate, and complete reporting and analysis of safety information from clinical studies are crucial for the protection of subjects, investigators, and the sponsor, and are mandated by regulatory agencies worldwide.

11.1. Definitions

11.1.1. Adverse Events

An AE is any untoward medical occurrence in a subject administered a pharmaceutical product and which does not necessarily have a causal relationship with this treatment. An AE can therefore be any unfavorable and unintended sign (including a clinically significant abnormal laboratory finding, for example), symptom, or disease temporally associated with the use of an investigational study drug, whether or not considered related to the study drug ([ICH-E2A, 1995](#)).

For the purposes of this clinical study, AEs include events which are either new or represent detectable exacerbations of pre-existing conditions.

The term “disease progression” should not be reported as an adverse event term. As an example, “worsening of underlying disease” or the clinical diagnosis that is associated with disease progression should be reported.

Adverse events may include, but are not limited to:

- Subjective or objective symptoms provided by the subject and/or observed by the Investigator or study staff including laboratory abnormalities.
- Any AEs experienced by the subject through the completion of final study procedures.
- AEs not previously observed in the subject that emerge during the protocol-specified AE reporting period, including signs or symptoms associated with the underlying disease that were not present before the AE reporting period
- Complications that occur as a result of protocol-mandated interventions (eg, invasive procedures such as biopsies).

The following are NOT considered AEs:

- **Pre-existing condition:** A pre-existing condition is not considered an AE unless the severity, frequency, or character of the event worsens during the study period.
- **Pre-planned or elective hospitalization:** A hospitalization planned before signing the informed consent form is not considered an SAE, but rather a therapeutic intervention. However, if during the pre-planned hospitalization an event occurs, which prolongs the hospitalization or meets any other SAE criteria, the event will be considered an SAE. Surgeries or interventions that were under consideration, but not performed before enrollment in the study, will not be considered serious if they are performed after enrollment in the study for a condition that has not changed from its baseline level. Elective hospitalizations for social reasons, solely for the administration of chemotherapy, or due to long travel distances are also not SAEs.
- **Diagnostic Testing and Procedures:** Testing and procedures should not to be reported as AEs or SAEs, but rather the cause for the test or procedure should be reported.

11.1.2. Serious Adverse Events

A serious adverse event based on ICH and EU Guidelines on Pharmacovigilance for Medicinal Products for Human Use is any untoward medical occurrence that at any dose:

- Results in death (ie, the AE actually causes or leads to death).
- Is life-threatening. Life-threatening is defined as an AE in which the subject was at risk of death at the time of the event. It does not refer to an event which hypothetically might have

caused death if it were more severe. If either the Investigator or the IND Sponsor believes that an AE meets the definition of life-threatening, it will be considered life-threatening.

- Requires in-patient hospitalization >24 hours or prolongation of existing hospitalization.
- Results in persistent or significant disability/incapacity (ie, the AE results in substantial disruption of the subject's ability to conduct normal life functions).
- Is a congenital anomaly/birth defect.
- Is an important medical event that may not result in death, be immediately life-threatening or require hospitalization, but may be considered an SAE when, based upon appropriate medical judgment, the event may jeopardize the subject or subject may require intervention to prevent one of the other outcomes listed in this definition. Examples of such events are intensive treatment in an emergency department or at home for allergic bronchospasm, blood dyscrasias, or convulsion that does not result in hospitalization; or development of drug dependency or drug abuse.

11.1.3. Severity Criteria (Grade 1-5)

Definitions found in the Common Terminology Criteria for Adverse Events version 4.03 (CTCAE v4.03) will be used for grading the severity (intensity) of *nonhematologic* AEs. The CTCAE v4.03 will be used for the grading of hematologic AEs when applicable. The CTCAE v4.03 displays Grades 1 through 5 with unique clinical descriptions of severity for each referenced AE. Should a subject experience any AE not listed in the CTCAE v4.03, the following grading system should be used to assess severity:

- Grade 1 (Mild AE) – experiences which are usually transient, requiring no special treatment, and not interfering with the subject's daily activities
- Grade 2 (Moderate AE) – experiences which introduce some level of inconvenience or concern to the subject, and which may interfere with daily activities, but are usually ameliorated by simple therapeutic measures
- Grade 3 (Severe AE) – experiences which are unacceptable or intolerable, significantly interrupt the subject's usual daily activity, and require systemic drug therapy or other treatment
- Grade 4 (Life-threatening or disabling AE) – experiences which cause the subject to be in imminent danger of death
- Grade 5 (Death related to AE) – experiences which result in subject death

11.1.4. Causality (Attribution)

The Investigator is to assess the causal relation (ie, whether there is a reasonable possibility that the study drug caused the event) using the following definitions:

Not Related (unrelated): Another cause of the AE is more plausible; a temporal sequence cannot be established with the onset of the AE and administration of the investigational product; or, a causal relationship is considered biologically implausible.

Unlikely: The current knowledge or information about the AE indicates that a relationship to the investigational product is unlikely.

Possibly Related: There is a clinically plausible time sequence between onset of the AE and administration of the investigational product, but the AE could also be attributed to concurrent or underlying disease, or the use of other drugs or procedures. Possibly related should be used when the investigational product is one of several biologically plausible AE causes.

Related: The AE is clearly related to use of the investigational product.

11.2. Unexpected Adverse Events

An “unexpected” AE is an AE that is not listed in the Investigator's Brochure/package insert or is not listed at the specificity or severity that has been observed. For example, hepatic necrosis would be “unexpected” (by virtue of greater severity) if the Investigator's Brochure referred only to elevated hepatic enzymes or hepatitis. Similarly, cerebral thromboembolism and cerebral vasculitis would be “unexpected” (by virtue of greater specificity) if the Investigator's Brochure/package insert listed only cerebral vascular accidents. "Unexpected" also refers to AEs that are mentioned in the Investigator's Brochure as occurring with a class of drugs or as anticipated from the pharmacological properties of the drug, but are not specifically mentioned as occurring with the study drug under investigation.

11.3. Special Reporting Situations

Special reporting situation on a Sponsor study may require expedited reporting and/or safety evaluation include, but are not limited to:

- Overdose of any study drug
- Suspected abuse/misuse of a study drug
- Inadvertent or accidental exposure to a study drug

- Medication error involving a product (with or without subject exposure to the study drug, e.g., name confusion)

If any special reporting situations meet the criteria of an AE, it should be reported on the Serious Adverse Event Report Form. The Serious Adverse Event Form should be sent via email or fax to Pharmacyclics Drug Safety or designee within 15 days of awareness.

11.4. Documenting and Reporting of Adverse Events and Serious Adverse Events by Investigators

11.4.1. Assessment of Adverse Events

Investigators will assess the occurrence of adverse events and serious adverse events at all subject evaluation timepoints during the study. All adverse events and serious adverse events whether volunteered by the subject, discovered by study personnel during questioning, detected through physical examination, all abnormal laboratory values, or other means, will be recorded. Each recorded adverse event or serious adverse event will be described by its duration (ie, start and end dates), severity, regulatory seriousness criteria (if applicable), suspected relationship to the investigational product, and any actions taken.

11.4.2. Adverse Event Reporting Period

All AEs whether serious or non-serious, will be captured from the time signed and dated ICF is obtained until 30 days following the last dose of study drug.

Serious adverse events reported after 30 days following the last dose of study drug should also be reported if considered related to study drug. Resolution information after 30 days should be provided.

Progressive disease should NOT be reported as an event term, but instead symptoms/clinical signs of disease progression may be reported. (See Section 11.1.1)

All adverse events, regardless of seriousness, severity, or presumed relationship to study drug, must be recorded using medical terminology in the source document. All records will need to capture the details of the duration and the severity of each episode, the action taken with respect to the study drug, investigator's evaluation of its relationship to the study drug, and the event outcome. Whenever possible, diagnoses should be given when signs and symptoms are due to a common etiology (eg, cough, runny nose, sneezing, sore throat, and head congestion should be reported as "upper respiratory infection").

All deaths should be reported with the primary cause of death as the AE term, as death is typically the outcome of the event, not the event itself.

If a death occurs within 30 days after the last dose of study drug, the death must be reported as a serious adverse event.

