5.3.3. Management of Nivolumab-Specific Adverse Events

Toxicities associated or possibly associated with nivolumab treatment should be managed according to standard medical practice. Additional tests, such as autoimmune serology or biopsies, may be used to determine a possible immunogenic etiology.

Although most immune-related adverse events observed with immunomodulatory agents have been mild and self-limiting, such events should be recognized early and treated promptly to avoid potential major complications. Discontinuation of nivolumab may not have an immediate therapeutic effect and in severe cases, immune-related toxicities may require acute management with topical corticosteroids, systemic corticosteroids, mycophenolate, or TNF- α inhibitors.

The primary approach to Grade 1-2 immune-related adverse events is supportive and symptomatic care with continued treatment with nivolumab; for higher grade immune-related adverse events, nivolumab should be held and oral/parental steroids administered. Recurrent Grade 2 immune-related adverse events may also mandate holding nivolumab or the use of steroids. Consideration for benefit/risk balance should be made by the investigator, with consideration of the totality of information as it pertains to the nature of the toxicity and the degree of clinical benefit a given patient may be experiencing prior to further administration of nivolumab. Nivolumab should be permanently discontinued in patients with life-threatening irAEs.

See Prescribing Information for full details.

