5.3.4.2. Gastrointestinal Toxicity

Immune-mediated colitis has been associated with the administration of nivolumab. Diarrhea or colitis was reported in 21% of patients in two trials of nivolumab. Immune-mediated colitis occurred in 2.2% of patients in one trial- of these one patient had Grade 2 colitis, and five had Grade 3 colitis. In the other trial, Grade 3 immune-mediated colitis occurred in 0.9% of patients.

Patients should be advised to inform the investigator if any diarrhea occurs, even if it is mild. Range for time to onset of symptoms of colitis has been 1-6 months.

If the event is of significant duration or magnitude or is associated with signs of systemic inflammation or acute phase reactants (e.g. increased CRP or platelet count or bandemia), it is recommended that sigmoidoscopy (or colonoscopy, if appropriate) with colonic biopsy with three to five specimens for standard paraffin block be performed.

Treatment may be restarted following the resolution of colitis. In addition, if the patient is being managed with corticosteroids, treatment should not be restarted until the steroids have been tapered down to a prednisone dose \leq 10 mg/day. Patients who resume treatment should be monitored closely for signs of renewed diarrhea.

Table 2 provides a summary of dose modification guidelines for gastrointestinal toxicities.

Table 2 Dose Modification Guidelines for Gastrointestinal Toxicity

Symptoms	Management	Follow-up
Grade 1 diarrhea: <4 stools per day over baseline Grade 1 colitis: asymptomatic colitis	Continue nivolumab Administer symptomatic treatment	
 - Close monitoring for worsening symptoms - Educate patients to report worsening immediately
Grade 2 diarrhea: 4-6 stools per day over baseline 
 - IV fluids indicated <24 hrs - Not interfering with ADL Grade 2 Colitis: abdominal pain, blood in stool	Withhold nivolumab Administer symptomatic treatment If symptoms persist >5 days or recur: 0.5 to 1 mg/kg/day prednisone equivalents	
If improved:
 
 - resume nivolumab - if steroids have been administered, taper steroids over at least 1 month before resuming nivolumab 
If symptoms worsen or persist >3-5 days with oral steroids:
 
 - treat as Grade 3 or 4

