7.1.1.5. Adverse Events

The accepted regulatory definition for an adverse event is provided in Section 11.1. All medical occurrences that meet the adverse event definition will be documented in the source documents from the time of first dose of study treatment until 30 days following the last dose of study drugs. SAEs will be reported to the Pharmacyclics and the study sponsor from the time of first dose of study treatment.

Both serious and non-serious AEs will be recorded in the CRF from the first dose of study drug until 30 days after the last dose of study drug(s).

Additional important requirements for adverse event and serious adverse event reporting are explained in Section 11.

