8.3. Follow-up Phase

Once a subject has completed the End-of-Treatment Visit they will enter the Follow-up Phase. Once subjects experience TF, relapse, or start use of alternative anticancer therapy (for subjects who have not withdrawn consent), they will be contacted approximately every 3 months (± 14 days) by clinic visit or telephone until death, subject withdrawal, lost to follow-up, study termination by the study sponsor, or up to 6 months whichever occurs first.

- Survival status, including other malignancies
- Subsequent anticancer therapy

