14. APPENDICES

Appendix 1. Schedule of Assessments

Study Visits	Screening Phase	Treatment Phase (1 cycle = 28 days)							Suspected PD	End-of-Treatment ^a	FU ^b
		Cycle 1		Cycle 2		Cycles 3–7		Cycles 8 and beyond			
		D1 (baseline)	D15	D1	D15	D1	D15	D1			
Study Visit Windows	-28 days			± 3 days					Any time	30 days after treatment d/c	q 3 mos
Informed consent	X										
Confirm eligibility	X	X									
Medical history	X										
Review concomitant medications	X	X	X	X	X	X	X	X		X	
Review adverse events ^c			X	X	X	X	X	X		X	
Study drug compliance review ^d			X	X	X	X		X			
Height	X										
Physical exam, vital signs, weight, ECOG	X	X	X	X	X	X		X	X	X	X
Disease assessment [†] :											
CT/MRI scan	X					X		X	X		X
Overall response assessment						X		X	X		X
Hematology	X	X	X	X	X	X	X	X	X	X	
Serum chemistry [*]	X	X	X	X		X		X	X	X	
TSH ^f	X	X				X		X		X	
Creatinine clearance (Cockcroft-Gault)	X									X	
PT/INR and PTT	X										
Hepatitis serologies	X										
Pregnancy test	X	X									
12 lead ECG	X	As clinically indicated [‡]									
Urine test	X										
Archival Specimen	X										
Blood for Translational Studies ^e	X		X							X	
Urine for Translational Studies	X		X							X	
Any new anticancer therapy											X
Study Drug Administration											
Nivolumab infusion		Every 2 weeks									
Ibrutinib (continuous)		X	X	X	X	X	X	X			

Abbreviations: D = day; d/c = discontinuation; PD = progressive disease; FU = follow-up, TSH = thyroid stimulating hormone.

Nivolumab: 240 mg IV every 2 weeks

[†]Disease assessment to be performed every 8 weeks

*Laboratory testing prior to Nivolumab treatment (will be done before every 2 doses of Nivolumab treatment, every 4 weeks).

[‡]ECG's may be performed at the investigator's discretion, particularly in subjects with arrhythmic symptoms (eg, palpitations, lightheadedness) or new onset dyspnea

a. An EOT visit will occur 30 ± 7 days from the last dose of study drug or prior to the start of a new anticancer treatment.

b. Once subjects experience TF, relapse, or start use of alternative anticancer therapy (for subjects who have not withdrawn consent), they will be contacted approximately every 3 months (±14 days) by clinic visit or telephone until death, subject withdrawal, lost to follow-up, study termination by the study sponsor, or up to 6 months whichever occurs first.

c. AEs are reported from the time the patient signs the Informed Consent Form until 30 days following last dose of study drug.

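### Routine adverse-event capture ends 30 days after the last dose and no follow-up contact lists an adverse-event question, so late non-serious immune events in early stoppers go uncollected

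*Combined protocol and SAP*

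**What the plan says.** **Capture window.** Three places end routine capture at the same point.
- Section 11.4.2: all adverse events, serious or not, "will be captured from the time signed and dated ICF is obtained until 30 days following the last dose of study drug".
- Section 7.1.1.5: "Both serious and non-serious AEs will be recorded in the CRF from the first dose of study drug until 30 days after the last dose".
- Appendix 1, footnote c: "AEs are reported from the time the patient signs the Informed Consent Form until 30 days following last dose of study drug".

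The start differs (consent in two places, first dose in 7.1.1.5), but the end does not.

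**Exception for serious events.** Section 11.4.2 continues: "Serious adverse events reported after 30 days following the last dose of study drug should also be reported if considered related to study drug". No end date is given for this duty. It also asks for resolution information after day 30.

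**Existing toxicity.** Section 3.2 follows patients for 30 days or until clinically significant treatment-related toxicity settles to grade 1 or less.

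**Follow-up contacts.** Section 8.3 sets contacts about every 3 months for up to 6 months, by clinic visit or telephone, once there is treatment failure, relapse or new anticancer therapy. It lists two items: "Survival status, including other malignancies", and later anticancer treatment. In Appendix 1 the adverse-event review row has no mark under follow-up. The same column does mark physical examination, vital signs, weight, ECOG, CT/MRI and response assessment.

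**General rule.** Section 11.4.1 has investigators assess adverse events at every subject evaluation timepoint.

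**Expected timing.** Section 5.3.4.2: "Range for time to onset of symptoms of colitis has been 1-6 months". Colitis is the only immune toxicity for which the protocol gives an onset range.

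**The concern.** The protocol's own onset range runs past the end of its collection window for anyone who stops both drugs early. A patient who stops at the week-8 scan leaves routine capture before month 3, about a third of the way through that range.

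Safety is the secondary objective (2.2) and a secondary endpoint (10.2.2). Section 10.5 summarises adverse events by organ class and grade, overall and by dose, and says nothing about unequal observation time. Events that fall after the window are lost selectively from early stoppers, so the reported frequency of late immune toxicity can only be pushed downward.

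**Working it through.** The plan states no figure on this point, so there is none to reproduce. The check compares the passages, then the windows.

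**1. Which late events are caught?** For a new event more than 30 days after the last dose of study drug:

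| Event | Reporting rule (11.4.2) | CRF (7.1.1.5) | Listed follow-up question (8.3, Appendix 1) |
|---|---|---|---|
| Serious, related | Reportable | Outside window | None |
| Serious, judged unrelated | Not covered | Outside window | None |
| Non-serious, any grade | Not covered | Outside window | None |
| New malignancy | Reportable (11.4.4) | Not stated | Yes |

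The protocol thus extends late capture for malignancies but not for immune events. In 12.7 the adverse-event form is tied to cycle completion. A follow-up form exists, but its content is not given.

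**2. How much of the 1-6 month range is covered?** Assume that onset is counted from first dose, and take 30.44 days per month. For a last dose on day d, the window ends at E = (d + 30)/30.44 months. The share of the range covered is (E - 1)/5, limited to 0-100%.

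| Last dose (day) | Window ends (day) | Months | Share covered |
|---|---|---|---|
| 1 | 31 | 1.02 | 0% |
| 28 | 58 | 1.91 | 18% |
| 56 | 86 | 2.83 | 37% |
| 84 | 114 | 3.75 | 55% |
| 112 | 142 | 4.67 | 73% |
| 140 | 170 | 5.59 | 92% |
| 153 | 183 | 6.01 | 100% |

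Full coverage needs a last dose at t = 6 - 30/30.44 = 5.01 months or later.

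**3. How many patients stop before then?** Assume exponential stopping times and stopping at progression only. With 6-month PFS rate S, the share stopping before t is 1 - S^(t/6). With median m, it is 1 - 0.5^(t/m).

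| Input | Source | Share stopping before 5.01 months | Of 30 |
|---|---|---|---|
| S = 0.70 | 10.3, target | 1 - 0.70^0.836 = 25.8% | 7.7 |
| S = 0.40 | 10.3, historical | 1 - 0.40^0.836 = 53.5% | 16.1 |
| m = 4.2 months | 1.1.1, nivolumab alone | 1 - 0.5^1.194 = 56.3% | 16.9 |
| m = 4.0 months | 1.1.1 | 1 - 0.5^1.254 = 58.1% | 17.4 |
| m = 2.7 months | 1.1.1 | 1 - 0.5^1.857 = 72.4% | 21.7 |

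**4. How many events might that be?** Section 5.3.4.2 gives immune-mediated colitis at 2.2% in one nivolumab trial and Grade 3 immune-mediated colitis at 0.9% in another. In 30 patients that is 30 x 0.022 = 0.66 and 30 x 0.009 = 0.27 cases in total. Only a fraction of these would start after the window closed. The rates for the combination, and the timing of other immune events, are not in the documents.

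**The case against.** The strongest reply is that the window is a deliberate and consistent choice with a safety valve, and that follow-up is not empty. Much of this stands.

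- A reader might infer that all new adverse events go unrecorded after day 30. They do not: a later serious event "should also be reported if considered related to study drug", and the important-medical-event clause in 11.1.2 lets the investigator classify an event as serious without hospitalisation.
- A reader might infer that no scheduled contact could reveal a late event. The follow-up column includes examination and imaging, and 11.4.1 calls for assessment at every evaluation timepoint. Even so, 8.3 allows the contact to be a telephone call, the adverse-event cell is blank, and 11.4.2 would still place a new non-serious event outside capture. The passages conflict.
- A reader might take "Discontinuation of nivolumab may not have an immediate therapeutic effect" in 5.3.3 as evidence of onset after stopping. It concerns immune toxicity already present, which 3.2 and 11.4.2 already follow to resolution.
- A reader might assume that every stop for toxicity closes the window. Sections 3.2.1 and 8.2 allow nivolumab alone, and 9.2 allows ibrutinib alone. The window runs from the last dose of study drug, so dropping one agent need not end capture.
- The 1-6 months is a range of observed colitis cases, not a distribution, and its origin is unstated. It cannot be carried over to other immune events.

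The replies do not reach the non-serious events, the CRF cut-off for late serious events, or the missing follow-up question.

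**Conclusion.** The point holds in a limited form. New non-serious immune-related events more than 30 days after the last dose fall outside collection. Late related serious events are reportable, but no listed question looks for them, and the CRF cut-off may keep them out of the safety tables. Late toxicity in patients who stop early may therefore be under-counted.

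Incomplete coverage of the stated colitis range affects about a quarter of patients if the trial meets its PFS target, about half at the historical rate, and 56-72% at the nivolumab-alone medians. This rests on onset counted from first dose, exponential stopping times, and both drugs stopping at progression only; the documents give none of these. The shares count shortened observation, and reading them as rates of missed events would be wrong. On the protocol's own colitis rates, the expected number missed is well below one. The case for change is that the loss runs in one direction, falls on a secondary endpoint, and is cheap to prevent.

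**What to change.** 1. In 8.3 and the follow-up column of Appendix 1, add an adverse-event question covering new immune-related events of any seriousness and related serious events. Ask it at 3-monthly contacts for every patient, from End of Treatment to the existing 6-month limit, and state where the 6 months start. Counted from the last dose or later, this takes even a patient who stops on day 1 to about month 6.
2. In 7.1.1.5, 11.4.2 and footnote c, extend the CRF and capture window for treatment-related events to match, and reconcile these passages with 11.4.1.
3. In 10.5, tabulate events after day 30, and events after new anticancer therapy, separately from the main 30-day summary.

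**Cost.** A few questions and one CRF field, plus some extra contacts for patients who stop without treatment failure, relapse or new therapy, since 8.3 triggers contacts only on those events. Attribution is less certain once new therapy has started; the separate table keeps that visible. Only data collection and reporting change.
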